5.2 Schedule of Events

Infants meeting the proposed eligibility criteria will be recruited. Written informed consent for the infants to participate will be obtained from parent(s)/LAR(s) prior to conducting any study procedures. **Table 3** describes the proposed schedule of study visits.

Table 3. Study Procedures.					
Procedure	Day -60 to Day 1	Day 1		Days 1-2	Days 3-14
Location of procedure	NICU	NICU		NICU	NICU or phone call
Group (Vaccinated, Unvaccinated, or Both)	Both	Vaccinated	Unvaccinated	Both	Vaccinated
Informed consent & Medical Release of Information	X				
Review Eligibility Criteria	X	X	X		
Demographic information	X				
Birth and delivery information	X				
General medical history		X	X		
Targeted medical history		X	X		
Respiratory support at time of randomization/vaccination		X	X		
Concomitant medications		X	X	X	X
Randomization		X	X		
Procedures				X	
Cardiorespiratory monitoring data capture				X	
Vaccination		X			
Clinically important adverse events		X	X	X	X
Serious adverse events		X	X	X	X

Study Day -60 to Day 1

- Obtain parental permission by written informed consent and a release of medical record information
- Review and confirm study eligibility, or likely study eligibility for pre-consent
- Obtain demographic, birth, and delivery information

Study Day 1

- Review and confirm study eligibility
- Obtain medical history both general and targeted (including respiratory support at time of randomization/vaccination and previous history of Hepatitis B vaccination)
- Obtain concomitant medication use within 1 week prior to randomization
- Randomize study participant to vaccination (vaccinated group) or no vaccination (unvaccinated group) (Section 5.5.1)
- Administer study vaccines to vaccination group. In order to limit differences between the two groups due to lag in vaccination after randomization, vaccines will be administered within 6 hours of randomization; however, vaccination up to 12 hours post-randomization will be permitted. A time window for vaccination is provided in order to allow for flexibility in coordination of vaccination with care/assessment times, family visits, other procedures.
- Record clinically important adverse events (including apnea) and serious adverse events

Study Days 1-2

- Cardiorespiratory monitoring (standard of care), with collection of printed or digital output
- Pulse oximetry monitoring (standard of care)
- Record concomitant medications

- Record standard of care procedures (including, but not limited to, any surgical procedures, eye exams, central line placements)
- Record clinically important adverse events (including apnea) and serious adverse events
- Of note, the unvaccinated group completes the study 48 hours after randomization.

Study Days 3-14 (Vaccinated group only)

**This period of time (day 3-14) will begin at 48 hours after vaccination.*

- Record clinically important adverse events (including apnea) and serious adverse events in vaccinated group only
 - If infant is discharged from the hospital prior to day 14, then follow-up of events will occur via telephone call with the parent/LAR and/or chart review of outpatient clinic notes or inpatient clinic notes (if infant is rehospitalized and these are available).

5.3 Parent/LAR Permission Process (Informed Consent)

The consent process will take place in the NICU or in a private conference room if preferred by the parent(s)/LAR(s). Initial discussions regarding the study may occur over the phone. Study staff will be available to answer all parent/LAR questions before and after permission is obtained. Parent(s)/LAR(s) will be given as much time as needed after being approached about their infant participating in the study and needing to decide whether or not to participate. We anticipate that the initial consent discussion, including presenting the information in the consent document and answering questions will take about 30 minutes. Parent(s)/LAR(s) will have the opportunity to take the consent form home and discuss the document with other family members or friends. During the consent process, it will be emphasized that participation is voluntary and that parents can withdraw permission for their infant to participate at any time. Permission will not be obtained from parent(s)/LAR(s) who do not read, who are blind, or who do not read/understand English or Spanish. Parent(s)/LAR(s) will be given a copy of the signed informed consent to take home with them. The original copy of the consent will be kept in the study records and a third copy will be included in the infant's medical record per local requirements.

5.4 Data Collection

Study staff will collect participant data at times according to **Table 1**.

Demographic information

The participant's postnatal age (days), race/ethnicity, sex, and insurance payer status will be obtained from the electronic health record (EHR) at the time of randomization.

Birth and delivery information

The subject's birth and delivery information including gestational age, birth weight, multiple birth, reason/indication for premature delivery will be captured from the EHR.

Medical history

The participant's medical history including but not limited to the following (apnea of prematurity, respiratory support at 36+0 weeks postmenstrual age (if $\geq 36+0$ weeks postmenstrual age at randomization), necrotizing enterocolitis, intraventricular hemorrhage and grade, periventricular leukomalacia, and seizures) be captured by the EHR. Current weight will also be recorded.

Respiratory support at time of randomization/vaccination

Respiratory support at time of randomization in the unvaccinated group and vaccination in the vaccinated group, including mode (noninvasive positive pressure ventilation, continuous positive airway pressure (CPAP), nasal cannula >1 liters per minute, nasal cannula <1 LPM, or none) and fraction of inspired oxygen (FiO₂), will be obtained from the EHR.

Concomitant medications

The participant's exposure to all prescribed medications in the 1 week prior to randomization will be obtained from the EHR. Start and stop dates will be collected. In addition, caffeine and acetaminophen administration will be collected during the study period with start/stop dates.

Cardiorespiratory monitoring data capture

All participants will have data captured from their continuous cardiorespiratory and pulse oximetry monitoring after randomization. Capture of continuous monitoring data will begin at randomization and end at 48 hours after vaccination (vaccinated group) or randomization (unvaccinated group). If infants in the vaccinated group are not vaccinated by 12 hours after randomization, capture of monitoring data will end at 60 hours after randomization. At the end of the 48-hour monitoring period, study staff at all enrolling sites will collect digital or printed output of data from cardiorespiratory monitors for all infants and send to the analysts at Duke University who will be blinded to the randomization group of the participants. To ensure the analysts are blinded to the treatment arms, the data obtained from the monitor for each infant will not include any personal or study identifiable information. Each output will be assigned a non-sequential coded number before they are sent to the analysts. The blinded analysis will interpret the output and record the date, time, and duration of each cardiorespiratory event (apnea, bradycardia, desaturation, and severe cardiorespiratory event) as defined below.

Procedures

[figure not shown]
Any procedures done as part of routine care (including, but not limited to, surgical procedures, eye exams, and central line placements) that occur beginning at randomization and ending at 48 hours after vaccination (vaccinated group) or randomization (unvaccinated group) will be recorded. Procedures occurring >60 hours after randomization in the vaccinated group will not be recorded. Data recorded will include the type of procedure, date/time of the procedure, length of the procedure, and a narrative describing any other important clinical information regarding the procedure.

Clinically important adverse events: days 1-2

Clinically important adverse events will be collected from randomization to 48 hours following randomization (unvaccinated group) or vaccination (vaccinated group). The following clinically important adverse events will be collected:

1. Apnea (*POM 1.1, SOM 1.1, SOM 1.2*)

- a. *Definition:* Apnea will be defined as a pause in respirations of >20 seconds, or a pause in respirations of >15 seconds with associated bradycardia (heart rate <80 beats per minute).
 - b. *Method of collection:* Obtained from the cardiorespiratory monitor as described above.
2. Increase in mode of respiratory support (SOM 1.3)
 - a. *Definition:* Increase in mode of respiratory support will be defined as progression from any lower level at baseline (at time of randomization in the unvaccinated group and vaccination in the vaccinated group) to any higher level (**Figure 2**). In addition, any increase in nasal cannula flow rate, or continuous positive airway pressure (CPAP) will be considered an increase in mode of respiratory support.
 - b. *Method of collection:* Respiratory data will be collected from the EHR daily, and the highest level of support that is maintained for >1 hour will be recorded. In addition, start/stop date/time for NIPPV and mechanical ventilation will be recorded.
 3. Severe cardiorespiratory event (SOM 2.1)
 - a. *Definition:* Respiratory pause of >30 seconds in duration or bradycardia of <60 beats per minute for >10 seconds
 - b. *Method of collection:* Obtained from the cardiorespiratory monitor as described above.
 4. Positive pressure ventilation delivered via bag-valve mask (SOM 2.2)
 - a. *Definition:* Infant with unexpected clinical decompensation requiring positive pressure ventilation via bag-valve mask.
 - b. *Method of collection:* Obtained from the EHR as documented by a clinical provider (e.g., physician, nurse, respiratory therapist).
 5. Fever (EOM 1.1)
 - a. *Definition:* Elevated temperature $\geq 38^{\circ}\text{C}$.
 - b. *Method of collection:* Highest daily temperature will be recorded from the EHR, in addition to how the temperature was obtained (skin, axillary, rectal, etc.) and infant's environment (open crib, radiant warmer or isolette).
 6. Hypothermia (EOM 1.2)
 - a. *Definition:* Decreased temperature $< 36^{\circ}\text{C}$.
 - b. *Method of collection:* Lowest daily temperature will be recorded from the EHR, in addition to how the temperature was obtained (skin, axillary, rectal, etc.) and infant's environment (open crib, radiant warmer or isolette).
 7. Oxygen desaturation (EOM 2.1)
 - a. *Definition:* Oxygen desaturation will be defined as a $\text{SpO}_2 < 88\%$ for >10 seconds.
 - b. *Method of collection:* Obtained from the cardiorespiratory monitor as described above.
 8. Bradycardia (EOM 2.2)
 - a. *Definition:* Bradycardia will be defined as a heart rate <80 beats per minute lasting >10 seconds.

- b. *Method of collection*: Obtained from the cardiorespiratory monitor as described above.
- 9. Blood culture for sepsis evaluation (*EOM 2.3*)
 - a. *Definition*: A sepsis work-up will be defined each day as a blood draw to obtain blood culture.
 - b. *Method of collection*: Data will be collected from the EHR (date/time of blood culture).
- 10. Antibiotics administered due to sepsis evaluation (*EOM 2.3*)
 - a. *Definition*: New receipt of intravenous or intramuscular antibiotics will be recorded if they were started in conjunction with a blood culture during the 48-hour monitoring period after vaccination in the “vaccinated” group and the 48-hour monitoring period after randomization in the “unvaccinated” group
 - b. *Method of collection*: Data will be collected from the EHR (date/time of start of the first new antibiotic).

Clinically important adverse events: days 4-14 (vaccinated group only)

- 1. Clinical apnea (*EOM 3.1*)
 - a. *Definition*: Clinical apnea will be defined as an apneic event that is documented by the nurse as part of standard care.
 - b. *Method of collection*: Events will be reviewed and collected from the EHR. Date, time, and duration of events will be noted when available from nursing documentation. Associated bradycardia and desaturation will be collected if available.
- 2. Increase in mode of respiratory support (*EOM 3.2*)
 - a. *Definition*: Increase in mode of respiratory support will be defined as progression from any lower level at baseline (end of study period on day 3) to any higher level (**Figure 2**). In addition, any increase in nasal cannula flow rate, CPAP pressure, or NIPPV pressure will be considered an increase in mode of respiratory support.
 - b. *Method of collection*: Respiratory data will be collected from the EHR daily, and the highest level of support that is maintained for >1 hour will be recorded.
- 3. Blood culture for sepsis evaluation (*EOM 3.3*)
 - a. *Definition*: A sepsis work-up will be defined as a blood draw to obtain blood culture.
 - b. *Method of collection*: Data will be collected from the EHR (date/time of blood culture).
- 4. Antibiotics administered due to sepsis evaluation (*EOM 3.3*)
 - a. *Definition*: New receipt of intravenous or intramuscular antibiotics will be recorded if they were started in conjunction with a blood culture
 - a. *Method of collection*: Data will be collected from the EHR (date/time of start of the first new antibiotic).
- 5. Positive pressure ventilation delivered via bag-valve mask (*EOM 3.4*)
 - a. *Definition*: Infant with unexpected clinical decompensation requiring positive pressure ventilation via bag-valve mask.
 - b. *Method of collection*: Obtained from the EHR as documented by a clinical provider (e.g., physician, nurse, respiratory therapist).
- 6. Hospital readmission (*EOM 3.5*)
 - a. *Definition*: Among infants who are discharged from the hospital, hospital readmission (yes/no) will be recorded along with date of readmission and reason for readmission. Scheduled, elective readmissions (e.g. surgical procedures) will not be counted.
 - b. *Method of collection*: Data will be collected from the EHR and/or follow-up phone call to parent/guardian

Serious adverse events (SAEs) (EOM 2.4)

An SAE is defined as an adverse event that results in one of the following outcomes during the infant's participation in the study:

- Results in death
- Is life-threatening (defined as immediate risk of death at the time of the event)
- Requires inpatient hospitalization (i.e. re-admission) or prolongation of inpatient hospitalization
- Results in a persistent or significant disability/incapacity
- Any other important medical event that may not result in death, be life threatening, or require hospitalization, may be considered an SAE when, based upon appropriate medical judgment, the event may jeopardize the subject and may require medical or surgical intervention to prevent one of the outcomes listed above.

Study site investigators will assess relatedness to study procedures and vaccines for all SAEs (related, possibly related, or unrelated).

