6.6 Analysis Plan

6.6.1 Pilot Study

The pilot phase of the study will include 12 infants. There will not be any formal analysis of study data. However, the feasibility benchmarks listed in **Table 5** will be documented for the first 12 patients to assess protocol adherence. These subjects will contribute to the final sample for analyses in the study objectives.

Table 5: Benchmarks for Pilot	
Benchmark	Target
Among pre-screened and eligible, LARs approached for consent	70%
Among approached for consent, consent obtained	40%
Documentation of reason for non-consent (of those approached)	80%
Among consent obtained, percent randomized	80%
Administration of vaccines in the vaccination group within 6 hours of randomization	60%
Administration of vaccines in the vaccination group within 12 hours of randomization	80%
Entire 48-hour monitoring period assessed for apnea events	80%

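### The planned length of the monitor record differs by arm, and neither document says that length is hidden from the blinded apnea readers

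*Protocol*

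**What the plan says.** Protocol 5.4 (cardiorespiratory monitoring data capture) gives the two arms different windows: "Capture of continuous monitoring data will begin at randomization and end at 48 hours after vaccination (vaccinated group) or randomization (unvaccinated group". For a vaccinated-arm infant not vaccinated by 12 hours, "capture of monitoring data will end at 60 hours after randomization". SAP 4.1 repeats the arm-specific windows. On the lag, Protocol 5.2 says that "vaccines will be administered within 6 hours of randomization; however, vaccination up to 12 hours post-randomization will be permitted".

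Sites then send the monitor output for every infant to the readers. Two masking steps are described: "the data obtained from the monitor for each infant will not include any personal or study identifiable information", and "Each output will be assigned a non-sequential coded number before they are sent to the analysts". The readers are to "interpret the output and record the date, time, and duration of each cardiorespiratory event", so what they receive carries timing. Protocol 5.6.2 and SAP 4.4 add only that the readers are blinded to assignment, while staff, caregivers and parents are not.

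The SAP describes the later steps differently. Under 5.1, monitor files are processed in SAS to find the events of interest. Under 8.1, monitor-identified apneas are confirmed by a blinded manual review whose procedure is not set out. A flagged event that review does not confirm is not counted, and an event with no strip to review is counted as apnea. SAP 8.2 treats severe events that qualify only through a long respiratory pause in the same way. SAP 9, sensitivity analysis 2, reanalyzes PO-1 and SO-2 with every monitor-determined event counted, whatever the review found.

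**The concern.** Blinded reading is the main protection against assessment bias in a trial that is otherwise open label. No planned unvaccinated record exceeds 48 h. If whole records reach the readers as Protocol 5.4 describes, a record clearly longer than that marks the infant as vaccinated, and neither identifier removal nor a scrambled code changes this.

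The readers' judgment feeds directly into the primary endpoint. A reader who can infer the arm could confirm flagged events more readily, or less readily, in vaccinees. The first would exaggerate an effect of vaccination on apnea and the second would conceal one. The secondary counts and durations of apnea (SOM 1.1 and 1.2) use the same confirmed events.

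**Working it through.** **1. The plan's own figure.** Inputs (Protocol 6.5, SAP 4.2): 15% vs 30%, 135 per arm, two-sided 0.05, chi-square. The pooled proportion is 0.225.
- Null SE = √(2 × 0.225 × 0.775 / 135) = 0.0508.
- Alternative SE = √((0.15 × 0.85 + 0.30 × 0.70) / 135) = 0.0500.
- Power = Φ((0.15 − 1.96 × 0.0508) / 0.0500) = 84.3%, as stated, and 270 / 0.9 = 300.

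The sample size calculation is sound and is not at issue.

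**2. Record length.** Unvaccinated: 48 h. Vaccinated: 48 h + lag, or 60 h if not vaccinated by 12 h.

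| Lag | Record | Excess over 48 h |
|---|---|---|
| 1 h | 49 h | 2.1% |
| 3 h | 51 h | 6.25% |
| 6 h | 54 h | 12.5% |
| 12 h, or not vaccinated by then | 60 h | 25% |

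**3. How many records stand out.** Protocol Table 5 sets targets of 60% for "Administration of vaccines in the vaccination group within 6 hours of randomization" and 80% for "Administration of vaccines in the vaccination group within 12 hours of randomization". If these are only just met:
- 100 − 60 = 40% of vaccinated-arm records run past 54 h.
- Of that 40%, 80 − 60 = 20 points end between 54 h and 60 h, and 100 − 80 = 20 points end at 60 h.

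The share is smaller if sites do better.

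**4. Could the intended output be a 48 h extract?** Protocol 5.4 has output collected when the 48-hour monitoring period ends, which might suggest one. The ITT analysis needs randomization (R) to R + 48 h, and the mITT analysis needs vaccination (V) to V + 48 h. Together they need R to V + 48 h, so the longer vaccinated record must be captured. Whether it is cut before reading is not stated.

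**5. Illustration.** The documents give no reader error rates, so everything in this step except n, alpha and the 15% is assumed. Each flagged infant has k = 1 to 3 flagged events, read independently with confirmation probability 0.6, and counts if at least one is confirmed: I(c) = 1 − (1 − c)^k. A share s = 0.4 of vaccinees is recognized and read at c instead of 0.6. The flagged share is f = 0.15 / I(0.6), which fixes the control rate at 15%. With no true effect, vaccinated rate = f × [0.4 × I(c) + 0.6 × I(0.6)].

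Example, k = 1, c = 0.8: f = 0.15 / 0.6 = 0.25, and the rate is 0.25 × (0.4 × 0.8 + 0.6 × 0.6) = 17.0% against 15%. The rejection rate is by exact enumeration of two binomials with n = 135 each, Pearson chi-square, two-sided 0.05 (5.0% with no shift):

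| k | c = 0.7 | c = 0.8 | c = 0.5 | c = 0.4 |
|---|---|---|---|---|
| 1 | 5.6% | 7.3% | 5.6% | 7.5% |
| 2 | 5.1% | 5.4% | 5.2% | 6.2% |
| 3 | 5.0% | 5.0% | 5.1% | 5.5% |

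The model leaves out the rule that unreviewable events count as apnea. If, as a further assumption, 25% of flagged infants qualify that way (k = 1, 20-point shift), then f = 0.15 / (0.25 + 0.75 × 0.6) = 0.214. The vaccinated rate is 16.3% (c = 0.8) or 13.7% (c = 0.4), and false rejection falls to about 6%.

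**The case against.** The strongest reply is that this is silence on detail. Both documents say that the readers are blinded, and Protocol 5.4 states that purpose. The SAP's more specific account (software flags events, reviewers confirm strips) points away from whole-record reading, and an isolated strip does not show total length. The bias is also limited: the apnea definition is numeric, the SAP describes review as confirming flagged events and not as adding any, unreviewable events count automatically, and sensitivity analysis 2 removes the reader's decision for PO-1 and SO-2.

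Most of this stands, and it limits the point without removing it. The SAP never says that reviewers see only strips or that length is withheld, and Protocol 5.4 has readers interpreting each infant's output. Following the written procedure could therefore undo the stated blinding. Sensitivity analysis 2 can help expose selective confirmation, but it does not protect the primary analysis and does not cover SOM 1.1 or 1.2.

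A reader might go further in four ways that the documents do not support:
- *That the readers are unblinded.* The review procedure is not described, short lags give records close to 48 h, and gaps or early stops blur actual lengths.
- *That clock time alone reveals the arm.* It is a weak cue without the record's start and end, or several events from one infant.
- *That the error rate is badly inflated.* Large figures need nearly every vaccinee recognized, one flagged event per infant and a large reader shift. None of these has a source in the documents.
- *That sensitivity analysis 2 would settle the matter.* With no true effect its odds ratio is 1 only in expectation, and a single trial of this size would vary around that.

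**Conclusion.** The concern holds as a gap in the described masking. From the documents alone: planned records are 48 h against 48 h plus the lag, up to 60 h; output for each infant goes to the readers; neither stated safeguard hides length; and confirmation determines which reviewable flagged events enter the primary analysis. The 40% share past 54 h rests on pilot feasibility targets for 12 infants being only just met, so it does not forecast the full study.

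The size and direction of any bias are unknown. With 60% confirmation, a 10- to 20-point shift either way, 40% of vaccinees recognized and 1 to 3 events per infant, false rejection is about 5% to 8%. That range is illustrative and depends wholly on those assumptions. If review already uses strips that do not reveal record length, there is no bias by this route and only the text needs completing. The change is worth making because it is cheap and protects the one blinded step in the trial.

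**What to change.** In Protocol 5.4 and SAP 8.1, require that the material given to readers does not show record start, record end or total length. Either of two routes would do: event-level excerpts, or segments of a common fixed length cut by the staff who already code the output. Keep event times in the data file, and have a program or the statistician assign confirmed events to the ITT and mITT windows afterwards. If review already works this way, saying so is enough.

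Masking absolute clock time and limiting readers to flagged strips are optional. If clock time is masked, the instruction that readers record the date and time of each event must be amended to match.

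The cost is a short text change in each document, some export or masking work (mainly for printed output) and, if excerpts are used, less surrounding trace for the readers. Endpoint, sample size and clinical care are unchanged.

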EOM 2.3: Proportion of infants requiring blood culture for and/or antibiotics (intravenously or intramuscularly) in the setting of blood culture for sepsis evaluation in a 48-hour monitoring period after vaccination in the “vaccinated” group and a 48-hour monitoring period after randomization in the “unvaccinated” group.

EOM 2.4: Proportion of infants with a serious adverse event in a 48-hour monitoring period after vaccination in the “vaccinated” group and a 48-hour monitoring period after randomization in the “unvaccinated” group.

EOM 3.1: Proportion of hospitalized infants with ≥ 1 episode of clinical apnea between 48 hours and 14 days after vaccination.

EOM 3.2: Proportion of hospitalized infants requiring any increase in respiratory support between 48 hours and 14 days after vaccination.

EOM 3.3: Proportion of hospitalized infants requiring blood culture and/or antibiotics (intravenously or intramuscularly) in the setting of blood culture for sepsis evaluation in between 48 hours and 14 days after vaccination.

EOM 3.4: Proportion of hospitalized infants requiring positive pressure ventilation in between 48 hours and 14 days after vaccination.

EOM 3.5: Proportion of discharged infants readmitted to the hospital within 14 days of vaccination.

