4.2 Subject Exclusion Criteria

Subjects who meet any of the following criteria will not be eligible to participate in this study:

1. Receipt of DTaP, IPV, PCV13, or Hib prior to enrollment. Previous administration of the first dose of HBV is permitted
2. Anticipated receipt of any vaccine other than DTaP, IPV, HBV, PCV13, or Hib during the first 60 hours after randomization
3. History of a severe allergic reaction (e.g. anaphylaxis) to a previous dose of any hepatitis B vaccine
4. History of a severe allergic reaction (e.g. anaphylaxis) to any component of the vaccines used in the study including neomycin, yeast and polymyxin B
5. History of latex allergy
6. Fever ≥38°C within 48 hours prior to randomization*
**This may result in a temporary delay of randomization*
7. Active known respiratory infection within 48 hours prior to randomization*
**This may result in a temporary delay of randomization*
8. Active infection being treated with systemic antimicrobials*
**This may result in a temporary delay of randomization*
9. Requiring mechanical ventilation or support with nasal intermittent positive pressure ventilation (NIPPV)*
**This may result in a temporary delay of randomization*
10. History of unstable progressive neurologic disorder of unknown cause
11. Known cause of apnea other than apnea of prematurity
12. Cyanotic heart disease (congenital or acquired)

13. Major invasive medical or surgical procedure (including circumcision) within 48 hours prior to randomization or anticipated to have major invasive medical or surgical procedure during the first 60 hours after *randomization**
**This may result in a temporary delay of randomization*
14. Child or parent/LAR is an immediate relative of study staff or an employee who is supervised by study staff.
15. Any condition that would, in the opinion of the site investigator, place the participant at an unacceptable risk of injury or render the participant unable to meet the requirements of the protocol

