## **9 SENSITIVITY ANALYSES**

The following sensitivity analyses are planned:

- 1) Apneic events that cannot be adjudicated will be counted as non-apneic events, and the PO-1 and SO-2 (severe cardiorespiratory events) will be reanalyzed.
- 2) All apneic events determined by the cardiorespiratory monitor will be counted as apneic events, regardless of manual review, and the PO-1 and SO-2 (severe cardiorespiratory events) will be reanalyzed.
- 3) The following infants will be excluded from analysis and all objectives re-analyzed:
  - a. Infants with a major surgical procedure (including circumcision) during the study period.
  - b. Receipt of any intramuscular injection, including Synagis or a vaccine other than DTaP, IPV, HBV, PCV13, or Hib during the study period.

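### Procedure recording stops 48 hours after vaccination, where exploratory EOM 3.2 begins, so respiratory support given around a planned operation up to day 14 is counted and cannot be separated in the planned dataset

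*Protocol*

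**What the plan says.** **What is recorded.** Under Procedures, Protocol 5.4 collects routine-care procedures from randomization, "ending at 48 hours after vaccination (vaccinated group) or randomization (unvaccinated group) will be recorded". It then caps the vaccinated group: "Procedures occurring >60 hours after randomization in the vaccinated group will not be recorded". The schedule of events (Protocol 5.2) marks Procedures under Days 1-2 only.

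**What is counted.** Protocol 2.1 lists "EOM 3.2: Proportion of hospitalized infants requiring any increase in respiratory support between 48 hours and 14 days after vaccination". Protocol 5.4 defines the event as "progression from any lower level at baseline (end of study period on day 3) to any higher level", and continues: "In addition, any increase in nasal cannula flow rate, CPAP pressure, or NIPPV pressure will be considered an increase in mode of respiratory support". The highest level held for more than 1 hour is recorded daily from the EHR. That duration is the only filter; no reason for the increase is required. SAP 8.3 lists the measure without any exception, SAP 8.4 repeats it by postmenstrual age group, and both test at an unadjusted 0.05.

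**How the neighboring measures treat planned care.** For EOM 3.5, "Scheduled, elective readmissions (e.g. surgical procedures) will not be counted". EOM 3.4 counts bag-mask ventilation only when the decompensation was unexpected.

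**Who can have surgery in the window.** Exclusion 13 in Protocol 4.2 keeps out an infant "anticipated to have major invasive medical or surgical procedure during the first 60 hours after" randomization. A later operation is no bar to entry.

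**What the SAP plans for surgery.** SAP 9 item 3 re-analyzes every objective after dropping certain infants. Item 3a is "Infants with a major surgical procedure (including circumcision) during the study period".

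**The concern.** EO 3 asks whether vaccinated infants with apnea in the first 48 hours do worse over the following days than those without. An infant taken to a scheduled operation on, say, day 8, who comes back on more support for some hours, meets EOM 3.2. So does an infant whose breathing worsened without any procedure. The analysis file will hold the support levels for both but nothing to tell them apart. Procedures are not collected in that window, and the only medications collected after randomization are caffeine and acetaminophen, so there is no anesthetic record to serve as a proxy.

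If such events occur equally in both subgroups, they pull the comparison toward no difference. If infants with early apnea also have more operations, the events push it the other way and can produce an apparent association. The surgery re-analysis in SAP 9 would be the natural check, but for this outcome window it lacks the data it needs.

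**Working it through.** **1. The plan's own figure.** Protocol 6.5 and SAP 4.2 give power only for the primary outcome: 15% v 30%, 135 per group, two-sided 0.05, 84.3%.
- Pooled rate 0.225; null SE = √(0.225 × 0.775 × 2/135) = 0.0508; alternative SE = √((0.15 × 0.85 + 0.30 × 0.70)/135) = 0.0500.
- z = (0.15 − 1.96 × 0.0508)/0.0500 = 1.01, so power is 84.3%. With 10% dropout, 270/0.90 = 300.

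Both figures reproduce and neither is in dispute. The documents give no rate or power for EOM 3.2.

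**2. Overlap of the two windows.** EOM 3.2 runs from 48 h to 14 days after vaccination: 336 − 48 = 288 h.
- Recording ends at 48 h after vaccination, so the overlap is 0 of 288 h.
- If the 60-hour cap is instead read as the working limit, the overlap is 12 h minus the delay from randomization to vaccination: 12/288 = 4.2% with no delay, 6/288 = 2.1% at 6 h, and 0 at 12 h.

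On either reading, at least 95.8% of the outcome window has no procedure record.

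**3. Equal procedure rates (illustration).** From the plan: 150 vaccinated infants (half of 300), 30% with early apnea, giving 45 v 105. Assumed: true EOM 3.2 rates t of 15% v 5%, and procedure-related support held for more than 1 hour in a fraction p of infants, independent of the true event. Observed rate = t + (1 − t)p. Infants counted only because of a procedure = (45 × 0.85 + 105 × 0.95)p = 138p, against 45 × 0.15 + 105 × 0.05 = 12 true events. Power is exact for Fisher's test, the test Protocol 6.2.2.3 names for EO 3 (SAP 8.3 names a stratified Mantel-Haenszel test).

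| p | Observed rates | Ratio | Difference (points) | Infants added | Power |
|---|---|---|---|---|---|
| 0 | 15.0% v 5.0% | 3.0 | 10.0 | 0 | 46% |
| 1% | 15.9% v 6.0% | 2.7 | 9.9 | 1.4 | 42% |
| 2% | 16.7% v 6.9% | 2.4 | 9.8 | 2.8 | 39% |
| 5% | 19.3% v 9.8% | 2.0 | 9.5 | 6.9 | 31% |
| 10% | 23.5% v 14.5% | 1.6 | 9.0 | 13.8 | 23% |

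A second set of assumptions gives the same pattern. With 40 v 95 infants (135 after dropout) and true rates of 20% v 5%, the odds ratio is 4.75. It falls to 3.7, 2.9 and 2.3 at p = 2%, 5% and 10%, and Fisher power falls from 69% to 61%, 52% and 41%.

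**4. Unequal procedure rates, no true difference (illustration).** Take t = 8% in both subgroups of 45 and 105.
- Procedures in 20% v 10%: 0.08 + 0.92 × 0.20 = 26.4% and 0.08 + 0.92 × 0.10 = 17.2%, a false ratio of 1.5. Fisher's test rejects about 23% of the time.
- Procedures in 5% v 2%: 12.6% and 9.8%, a false ratio of 1.3. Fisher's test rejects 6.5% of the time, close to nominal.

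**5. Whether item 3a can be carried out.** The SAP does not define *study period*. Protocol 5.4, in the EOM 3.2 baseline, places its end on day 3. Elsewhere in 5.4 caffeine and acetaminophen are collected during the study period, and the schedule of events continues concomitant medications through Days 3-14. Under the short reading, item 3a runs but leaves in infants operated on during the EO 3 window. Under the long reading, it calls for surgery dates that are not collected. Neither reading removes those infants.

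**The case against.** The best defense is that EOM 3.2 measures what its name says: any increase in support. SOM 1.3 has no procedure exception either, and the exceptions in EOM 3.4 and 3.5 show that the protocol could set planned care aside, not that it meant to here. Procedures can also follow deterioration, so discarding support around an operation could discard true events. This stands, and it argues against redefining the endpoint. It does not argue against knowing which events followed a procedure.

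Three further points limit the concern.
- A reader might infer that these events can never be identified. The documents do not support that. Support levels come from the EHR, so an event in a hospitalized infant can be traced to its chart, and SAE narratives may cover complicated operations. What is missing is any plan to collect the information.
- A reader might infer that item 3a fails outright. With *study period* ending on day 3, it can be run as written. The gap is in what it covers for EO 3.
- The illustrations may run high. No procedure rate is given, support of 1 hour or less is never scored, and EOM 3.2 is restricted to hospitalized infants, so the true denominators are below 150. At 1% to 2% the ratio hardly moves, and the risk difference is little changed even at 10%.

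Finally, apnea v no apnea within the vaccinated group is not a randomized comparison. If infants with early apnea are sicker, EO 3 is confounded whether or not procedures are recorded.

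**Conclusion.** The gap is real and narrow. Procedure recording ends where EOM 3.2 begins. The endpoint accepts any increase held for more than 1 hour, and the planned dataset cannot separate support given around a scheduled operation. The surgery re-analysis in SAP 9 does not reach this window.

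The size is unknown. Under assumed true rates of 15% v 5%, contamination of 1% to 10% would lower the ratio from 3.0 to between 2.7 and 1.6. Under Fisher's test the comparison has only 46% power even with no contamination. The direction rests on a further assumption: toward no difference if procedures are equally common in both subgroups, possibly toward a false association if they are commoner after early apnea.

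A reader might infer that the trial's main safety conclusions are at risk. They are not: the primary and secondary outcomes use the 48-hour window, in which procedures are recorded. This is a cheap improvement to one exploratory measure, not a flaw in the design.

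**What to change.** 1. Protocol 5.4 and the schedule of events: record procedure type and start date/time to day 14 in hospitalized vaccinated infants, during the EHR review already done daily for respiratory support. If follow-up is complete, abstract the same items retrospectively for infants with an EOM 3.2 event.
2. SAP 8.3 or 9: keep EOM 3.2 as defined, and add a prespecified sensitivity analysis that does not count increases begun for a scheduled procedure.
3. SAP 9 item 3a: state that for EO 3 the study period runs to day 14. This step needs surgery dates for all hospitalized vaccinated infants; abstraction limited to those with an EOM 3.2 event supports step 2 but not the full item 3a exclusion.

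The cost is slightly more chart abstraction in one arm and one added analysis. The change does not remove confounding between infants with and without early apnea, and the report of EO 3 should say so. If no abstraction is possible, the limitation should be reported with EOM 3.2.
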